6.1.2 Investigational Agent(s)

Nivolumab: No premedication indicated, may give Acetaminophen 500 mg po once prior to Nivolumab administration, which is optional.

Metformin: No premedication indicated. AM dose should be taken with breakfast and PM dose should be taken with dinner.

6.2 DOSING DELAYS/DOSE MODIFICATIONS

6.2.1 Metformin

The following guidelines are provided for the modification of the dose of metformin in the event of toxicities attributed by the investigator to this study drug. Toxicities unrelated to metformin will not ordinarily result in the modification of dose. AEs will be defined based on the National Cancer Institute (NCI) Common Terminology Criteria for Adverse Events (CTCAE) version 4.

In general, subjects experiencing **Grade 1 and 2** drug related toxicities should not have the dose of metformin modified. However, appropriate supportive care should be provided for the management of drug related toxicities. Grade 2 toxicities may require dose or schedule modifications (delaying or omitting individual doses) due to potentially greater clinical significance; however, this should occur after discussion with study PI.

Dosing of metformin must be delayed if a subject experiences a **Grade 3 non-hematologic** toxicity. If the toxicity resolves (returned to baseline or decreased to Grade ≤ 1) within 7 days, dosing of metformin may be resumed one lower dose level (See section 6 Table 3). Exceptions to this rule are as follows:

- Grade 3 fatigue: dose modification is left to the PI's discretion;

- Grade 3 nausea, vomiting and diarrhea: dose modification only after optimal prophylactic measures have failed to control the symptoms adequately;

In the case of Grade 4 **non-hematologic** toxicity, **or persistent Grade 3** toxicity despite one dose level reduction, metformin will be discontinued.

No dose adjustment of metformin will be performed for anemia.

No dose adjustment for Metformin will be performed for grade 1, 2, or 3 neutropenia or grade 1, 2, or 3(without bleeding) thrombocytopenia.

Dosing of metformin will be delayed if subjects develop grade 4 neutropenia or grade 3 thrombocytopenia complicated by bleeding or grade 4 thrombocytopenia. If the toxicity resolves (returned to baseline or decreased to Grade ≤ 1) within 14 days, dosing of metformin may be resumed one lower dose level (See section 6 Table 3).

Table 3: Dose reduction of Metformin

| Dose Level | Metformin |
|-------------------|------------------------|
| 1 | 1000 mg AM/1000 mg PM |
| -1 | 500 mg AM/1000mg mg PM |
| -2 | 500 mg AM/500mg mg PM |

6.2.2 Nivolumab

Adverse events (both non-serious and serious) associated with nivolumab exposure may represent an immunologic etiology. These adverse events may occur shortly after the first dose or several months after the last dose of treatment. nivolumab must be withheld for drug-related toxicities and severe or life-threatening AEs as per 3 below. See Section 6.6.1 for supportive care guidelines, including use of corticosteroids.

Toxicities unrelated to nivolumab will not ordinarily result in the modification of nivolumab dose. AEs will be defined based on the National Cancer Institute (NCI) Common Terminology Criteria for Adverse Events (CTCAE) version 4.

[figure not shown]
Dose Modification Guidelines for Drug-Related Adverse Events- Nivolumab

1. Corticosteroid taper should be initiated upon AE improving to Grade 1 or less and continue to taper over at least 4 weeks.
2. For situations where Nivolumab has been withheld, Nivolumab can be resumed after AE has been reduced to Grade 1 or 0 and corticosteroid has been tapered. Nivolumab should be permanently discontinued if AE does not resolve within 12 weeks of last dose or corticosteroids cannot be reduced to ≤ 10 mg prednisone or equivalent per day within 12 weeks.
3. For severe and life-threatening irAEs, IV corticosteroid should be initiated first followed by oral steroid. Other immunosuppressive treatment should be initiated if irAEs cannot be controlled by corticosteroids.

4. Myocarditis: Withhold treatment for Grade 1 or 2. Permanently discontinue for Grade 3 or 4. Based on severity of AE administer corticosteroids.
5. Newly developed Type I diabetes mellitus: Follow endocrinopathy adverse event management algorithm. Permanently discontinue Nivolumab if associated hyperglycemia is grade 4.
6. Dosing interruptions are permitted in the case of medical / surgical events or logistical reasons not related to study therapy (e.g., elective surgery, unrelated medical events, patient vacation, and/or holidays). Subjects should be placed back on study therapy within 3 weeks of the scheduled interruption, unless otherwise discussed with the Sponsor-investigator. The reason for interruption should be documented in the patient's study record.

GI Adverse Event Management Algorithm

[figure not shown]
Rule out non-inflammatory causes. If non-inflammatory cause is identified, treat accordingly and continue I-O therapy. Opiates/narcotics may mask symptoms of perforation. Infliximab should not be used in cases of perforation or sepsis.

Patients on IV steroids may be switched to an equivalent dose of oral corticosteroids (e.g. prednisone) at start of tapering or earlier, once sustained clinical improvement is observed. Lower bioavailability of oral corticosteroids should be taken into account when switching to the equivalent dose of oral corticosteroids.

Renal Adverse Event Management Algorithm

[figure not shown]
Rule out non-inflammatory causes. If non-inflammatory cause, treat accordingly and continue I-O therapy.

Patients on IV steroids may be switched to an equivalent dose of oral corticosteroids (e.g. prednisone) at start of tapering or earlier, once sustained clinical improvement is observed. Lower bioavailability of oral corticosteroids should be taken into account when switching to the equivalent dose of oral corticosteroids.

Pulmonary Adverse Event Management Algorithm

[figure not shown]
Rule out non-inflammatory causes. If non-inflammatory cause, treat accordingly and continue I-O therapy. Evaluate with imaging and pulmonary consultation.

Patients on IV steroids may be switched to an equivalent dose of oral corticosteroids (e.g. prednisone) at start of tapering or earlier, once sustained clinical improvement is observed. Lower bioavailability of oral corticosteroids should be taken into account when switching to the equivalent dose of oral corticosteroids

Hepatic Adverse Event Management Algorithm

Rule out non-inflammatory causes. If non-inflammatory cause, treat accordingly and continue I-O therapy. Consider imaging for obstruction.

[figure not shown]

Patients on IV steroids may be switched to an equivalent dose of oral corticosteroids (e.g. prednisone) at start of tapering or earlier, once sustained clinical improvement is observed. Lower bioavailability of oral corticosteroids should be taken into account when switching to the equivalent dose of oral corticosteroids.

*The recommended starting dose for grade 4 hepatitis is 2 mg/kg/day methylprednisolone IV.

Endocrinopathy Adverse Event Management Algorithm

[figure not shown]
Rule out non-inflammatory causes. If non-inflammatory cause, treat accordingly and continue I-O therapy. Consider visual field testing, endocrinology consultation, and imaging.

Patients on IV steroids may be switched to an equivalent dose of oral corticosteroids (e.g. prednisone) at start of tapering or earlier, once sustained clinical improvement is observed. Lower bioavailability of oral corticosteroids should be taken into account when switching to the equivalent dose of oral corticosteroids.

Skin Adverse Event Management Algorithm

Rule out non-inflammatory causes. If non-inflammatory cause, treat accordingly and continue I-O therapy.

[figure not shown]
Patients on IV steroids may be switched to an equivalent dose of oral corticosteroids (e.g. prednisone) at start of tapering or earlier, once sustained clinical improvement is observed. Lower bioavailability of oral corticosteroids should be taken into account when switching to the equivalent dose of oral corticosteroids.

*Refer to NCI CTCAE v4 for term-specific grading criteria.

[^]If SJS/TEN is suspected, withhold I-O therapy and refer patient for specialized care for assessment and treatment. If SJS or TEN is diagnosed, permanently discontinue I-O therapy.

Neurological Adverse Event Management Algorithm

Rule out non-inflammatory causes. If non-inflammatory cause, treat accordingly and continue I-O therapy.

Patients on IV steroids may be switched to an equivalent dose of oral corticosteroids (e.g. prednisone) at start of tapering or earlier, once sustained clinical improvement is observed. Lower bioavailability of oral corticosteroids should be taken into account when switching to the equivalent dose of oral corticosteroids.

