Nivolumab will be provided intravenously and metformin will be provided in tablet form. Eligible subjects will receive nivolumab 480 mg IV every 4 weeks and metformin 1000 mg po BID according to the study design.

Control therapy, dose and administration: N/A

Efficacy evaluation/Endpoints:

Primary Endpoint: ORR

Secondary Endpoints: To determine PFS, OS, and biochemical response (CEA), immune and metabolic biomarkers in tumor microenvironment and systemic circulation (pre and post research biopsy required)

Safety evaluation/Endpoints:

[figure not shown]
NCI Common Toxicity Criteria Version 4.0

Rationale for number of subjects: Primary objective is to determine the overall response rate. Historically ORR with single agent nivolumab in CRC is <5% and metformin and nivolumab combination will have ORR of 15%. Simon's MinMax two stage design is employed for the study with power of 80% and alpha of 0.1. If there is 1 response in first 18 patients in the first stage of the study, then it will proceed with second stage to enroll total of 28 patients. If there are 3 or more responders out of the 28 patients then it would be positive study. This will enable us to evaluate clinical endpoints (ORR, CEA, RFS, OS) as well as evaluate the impact on immune biomarkers.

Statistical methods: Phase II design

Translational Research: Correlative assays will include- immune profiling of TILs and circulating lymphocytes, plasma cytokine levels, and key metabolic biomarkers of relevance to mechanism of metformin action when administered in combination with immunotherapy. Paired biopsies will be obtained in all patients.

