8.3.2 Table 6 Evaluating Adverse Events

An investigator who is a qualified physician, will evaluate all adverse events as to:

| | | |
|---|--|---|
| V4.0 CTCAE Grading | Grade 1 | Mild; asymptomatic or mild symptoms; clinical or diagnostic observations only; intervention not indicated. |
| | Grade 2 | Moderate; minimal, local or noninvasive intervention indicated; limiting age-appropriate instrumental ADL. |
| | Grade 3 | Severe or medically significant but not immediately life-threatening; hospitalization or prolongation of hospitalization indicated; disabling; limiting self-care ADL. |
| | Grade 4 | Life threatening consequences; urgent intervention indicated. |
| | Grade 5 | Death related to AE |
| Seriousness | A serious adverse event is any adverse event occurring at any dose or during any use of investigational product that: | |
| | † Results in death; or | |
| | † Is life threatening; or places the subject, in the view of the investigator, at immediate risk of death from the event as it occurred (Note: This does not include an adverse event that, had it occurred in a more severe form, might have caused death.); or | |
| | † Results in a persistent or significant disability/incapacity (substantial disruption of one's ability to conduct normal life functions); or | |
| | † Results in or prolongs an existing inpatient hospitalization (hospitalization is defined as an inpatient admission, regardless of length of stay, even if the hospitalization is a precautionary measure for continued observation. (Note: Hospitalization for an elective procedure to treat a pre-existing condition that has not worsened is not a serious adverse event. A pre-existing condition is a clinical condition that is diagnosed prior to the use of investigational products and is documented in the patient's medical history.); or | |
| | † Is a congenital anomaly/birth defect (in offspring of subject taking the product regardless of time to diagnosis); or | |
| | Is a new cancer (that is not a condition of the study) (although not serious per ICH definition, is reportable to the Sponsor within 24 hours and to BMS within 2 working days to meet certain local requirements); or | |

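### Notes 2 and 4 of the nivolumab dose-modification guidelines give opposite answers for a myocarditis at Grade 1: note 2 permits redosing, note 4 requires a hold

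*Combined protocol and SAP*

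**What the plan says.** The dose-modification guidelines for nivolumab in section 6.2.2 consist, as printed, of six numbered notes. Three bear on this point.

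- Note 4 covers myocarditis: "Myocarditis: Withhold treatment for Grade 1 or 2. Permanently discontinue for Grade 3 or 4. Based on severity of AE administer corticosteroids". It contains no restart condition.
- Note 2 is the general restart rule after a hold for an adverse event: "Nivolumab can be resumed after AE has been reduced to Grade 1 or 0 and corticosteroid has been tapered". It is worded for every situation in which nivolumab was withheld. It continues: "Nivolumab should be permanently discontinued if AE does not resolve within 12 weeks of last dose", with a parallel stop if steroids cannot be brought down to 10 mg prednisone or equivalent per day within 12 weeks.
- Note 1 sets the taper: "Corticosteroid taper should be initiated upon AE improving to Grade 1 or less and continue to taper over at least 4 weeks".

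Note 5, the other event-specific note, sends the reader elsewhere: "Newly developed Type I diabetes mellitus: Follow endocrinopathy adverse event management algorithm". Note 4 gives no such pointer. The printed organ algorithms are gastrointestinal, renal, pulmonary, hepatic, endocrine, skin and, last, "Neurological Adverse Event Management Algorithm". None is cardiac.

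**The concern.** By giving myocarditis a separate note and withholding drug even at Grade 1, the plan treats it more cautiously than its general rule treats other events. If the general rule then governs the restart, that caution is lost: a patient whose myocarditis has improved only to Grade 1 could receive the next full dose (the synopsis states "Eligible subjects will receive nivolumab 480 mg IV every 4 weeks") at a grade where note 4 calls for a hold. What is at stake is patient safety and consistent handling of such a case. The response-rate analysis, the two-stage rule and the sample size are untouched.

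**Working it through.** No arithmetic applies. The check is to read notes 2 and 4 together at each state of a myocarditis and see whether they agree.

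| State of the myocarditis | Note 4 | Note 2 | Agree? |
|---|---|---|---|
| Grade 3 or 4 | Permanent stop | Not engaged; it concerns withheld drug | Yes |
| Grade 2 | Hold | Restart not allowed; grade too high | Yes |
| Improved to Grade 1, steroid not yet tapered | Hold | Restart not allowed; taper outstanding | Yes |
| Improved to Grade 1, steroid tapered | Hold | Restart allowed | **No** |
| Grade 0, steroid tapered | No hold grade applies | Restart allowed | Yes |

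The disagreement is confined to one row. An event that was Grade 1 from the start is also unclear, because note 2 speaks of an event that has been reduced to that grade.

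Three checks on whether other text removes the conflict:

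1. *The steroid condition.* Table 6 in section 8.3.2 describes Grade 2 generically as "Moderate; minimal, local or noninvasive intervention indicated; limiting age-appropriate instrumental ADL", and note 4 leaves steroids to severity. If steroids are given, the taper delays the restart but does not change the grade at which it is allowed. If none are given, there is nothing to taper and grade alone decides. The conflict survives either way.
2. *The 12-week clause.* It says when nivolumab must be abandoned, not the grade at which it may be restarted before then. It also turns on the event resolving, which is not defined for nivolumab. Section 6.2.1 defines the same term for metformin as a return to baseline or Grade 1 or lower, so a reader who carries that over would count Grade 1 as resolved.
3. *Other sections.* Section 6.6.1 refers back to section 6.2. The rechallenge entry in Table 6 requires advance sponsor approval in some cases, but by reference to the dose-modification guidelines, which leads back to these notes. Section 6.8 (investigator judgement) and section 11.5 (weekly review of toxicity logs) name no restart grade.

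**The case against.** The strongest objection is the missing figure. It sits directly above the heading of the guidelines, and the notes read like footnotes to a table. The lead-in to section 6.2.2 refers to an item 3 for when to withhold, yet printed note 3 deals only with steroids and other immunosuppression. A grade-by-grade schedule, possibly with a myocarditis row, may therefore be in the figure. This stands as a limit: the point concerns the printed notes only, and the absence of a printed cardiac algorithm is weak evidence about the full plan. It does not remove the conflict, because notes 2 and 4 would still disagree as worded.

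Second, the notes can be reconciled. Note 2 is permissive and general, note 4 directive and specific, so a careful reader would hold until Grade 0. That is a sensible reading, but no printed text gives note 4 precedence.

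Third, the practical risk is limited. This is a single-centre study of 28 patients. Table 6 requires prior sponsor approval where a serious event may have been caused by the product, or where re-exposure adds significant risk, and residual myocarditis plausibly meets the second condition. Toxicity logs are reviewed weekly. These safeguards stand and keep the point small.

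A reader might infer more than the documents support:

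- *That no restart rule exists for myocarditis.* Note 2 supplies one, with steroid and 12-week conditions. The fault is the clash at Grade 1.
- *That a redosing window before the 12-week limit can be calculated.* The 12 weeks govern resolution and steroid dose, not the date of the next dose. The plan also does not say that a resumed dose must fall on a fixed 28-day slot.
- *That redosing at Grade 1 has been shown to be unsafe.* The documents do not address this.

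**Conclusion.** The concern holds for the printed notes. For a myocarditis that has improved to Grade 1 with any steroid tapered, note 2 permits nivolumab and note 4 withholds it, and nothing printed says which prevails. The conflict covers one event at one grade. No frequency is claimed, because the documents give no myocarditis rate; no timing margin is claimed; and no statistical result is affected. It is a low-cost safety clarification.

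The conclusion assumes that note 2 means what it says in covering every hold, and that the figure not shown contains no overriding restart rule. If it does contain one, what remains is to bring the wording of the two notes into line with it.

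**What to change.** Add to note 2: *Exception: nivolumab withheld for Grade 1 or 2 myocarditis may resume only after the event has resolved to Grade 0 and any corticosteroid taper is complete.* Cross-refer to this from note 4. Grade 0 is proposed because it is the only grade at which note 4 neither withholds nor stops nivolumab. If the sponsor intends another threshold, stating it in note 4 and exempting myocarditis from note 2 would also remove the conflict. If the figure already holds a myocarditis restart rule, align notes 2 and 4 with it.

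The drafting cost is one clause and one cross-reference. The clinical cost is that a rare patient with persistent Grade 1 findings would not be redosed. Confirming Grade 0 may need an unscheduled cardiac test, since the study calendar in section 7 lists an ECG at screening only; section 8.1 already allows unscheduled procedures.

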6.3 General Concomitant Medication and Supportive Care Guidelines

Because there is a potential for interaction of *nivolumab* and *metformin* with other concomitantly administered drugs through the cytochrome P450 system, the case report form must capture the concurrent use of all other drugs, over-the-counter medications, or alternative therapies. The Principal Investigator should be alerted if the patient is taking any agent known to affect or with the potential to affect selected CYP450 isoenzymes.

Medications or vaccinations specifically prohibited in the exclusion criteria are not allowed during the ongoing trial. If there is a clinical indication for one of these or other medications or vaccinations specifically prohibited during the trial, discontinuation from trial therapy or vaccination may be required. The investigator should discuss any questions regarding this with the PI. The final decision on any supportive therapy or vaccination rests with the investigator and/or the subject's primary physician.

6.4 Acceptable Concomitant Medications

All treatments that the investigator considers necessary for a subject's welfare may be administered at the discretion of the investigator in keeping with the community standards of medical care. All concomitant medication will be recorded on the case report form (CRF)

including all prescription, over-the-counter (OTC), herbal supplements, and IV medications and fluids. If changes occur during the trial period, documentation of drug dosage, frequency, route, and date may also be included on the CRF.

All concomitant medications received within 28 days before the first dose of trial treatment and 30 days after the last dose of trial treatment should be recorded. Concomitant medications administered after 30 days after the last dose of trial treatment should be recorded for SAEs and ECIs (event of clinical interests) as defined in Section 8.2.

6.5 Prohibited Concomitant Medications

Subjects are prohibited from receiving the following therapies during the Screening and Treatment Phase (including retreatment for post-complete response relapse) of this trial:

- Antineoplastic systemic chemotherapy, monoclonal antibody or biological therapy
- Immunotherapy not specified in this protocol
- Investigational agents other than Nivolumab and Metformin
- Radiation therapy
 - Note: Radiation therapy to a symptomatic solitary lesion or to the brain may be allowed at the investigator's discretion. Nivolumab will be held during radiation and can be resumed after radiation is finished and patient is stable per the treating physician. Metformin can be resumed during radiation.
- Live vaccines within 30 days prior to the first dose of trial treatment and while participating in the trial. Examples of live vaccines include, but are not limited to, the following: measles, mumps, rubella, varicella/zoster, yellow fever, rabies, BCG, and typhoid vaccine.
- Systemic glucocorticoids for any purpose other than to modulate symptoms from an event of clinical interest or suspected immunologic etiology. The use of physiologic doses of corticosteroids may be approved after consultation with the Sponsor - investigator.
- Inhibitors of CYP3A4 and/or PgP

Co-administration with strong inhibitors of CYP3A4 (e.g., ketoconazole, itraconazole, ritonavir) is prohibited.

- Co-administration with moderate CYP3A4 inhibitors (e.g., erythromycin, fluconazole) or PgP inhibitors should be avoided.. Co-administration with moderate CYP3A4 can be done with caution and only if other alternatives are not available.
- Lists of CYP3A4 inducers and inhibitors can be found on: <http://medicine.iupui.edu/clinpharm/ddis/table.aspx> and <http://www.fda.gov/Drugs/DevelopmentApprovalProcess/DevelopmentResources/DrugInteractionsLabeling/ucm080499.htm>).
- Inducers of CYP3A4 and/or PgP

Strong CYP3A4 inducers (i.e., phenytoin, carbamazepine, rifampin, rifabutin, phenobarbital, St. John's wort) should only be used if alternatives are not available. Moderate inducers of CYP3A4 are allowed if alternatives are not available.

Subjects who, in the assessment by the investigator, require the use of any of the aforementioned treatments for clinical management should be removed from the trial. Subjects may receive other medications that the investigator deems to be medically necessary.

There are no prohibited therapies during the Post-Treatment Follow-up Phase.

